2. LAY SUMMARY

Backwards walking has been shown to improve balance and walking in patients who have knee Osteoarthritis. We don't know if these benefits may also be seen after surgery with patients who have had a hip or knee replacement because of Osteoarthritis. This study will look to see if it is possible to conduct a bigger study into how effective backwards walking may be after joint replacement. Patients who come to the Nuffield Orthopaedic Centre in Oxford for a hip or knee replacement will be invited. They will be placed into one of two groups at random: a group where they have a course of physiotherapy plus a backwards walking programme or a group where they have a course of physiotherapy. The physiotherapy will last for 12 weeks and those who take part will take part in two study assessments. The first will be before any treatment and patients will complete five measures and also be issued with a simple tick box diary to complete over the 12 weeks. The second assessment will be after the treatment and will involve the same 5 measures and the diaries will be collected in. Participants at this assessment will also be asked if they would like to take part in an interview for the study. This is to see what the patients thought of the study. During the study the researcher will record things like how many patients say 'yes' to the study and how many participants drop out of the treatment to understand if a bigger study could take place.

3. SYNOPSIS

Study Title	A Backwards Walking Programme following Hip and Knee Arthroplasty: A Feasibility Pilot Study		
Internal ref. no. / short title	Backwards Walking in patients following Knee and Hip Replacement		
Study registration			
Sponsor	Oxford University Hospitals NHS Foundation Trust		
Funder	N/A		
Study Design	Mixed methods feasibility pilot study		
Study Participants	Men and women who have undergone hip or knee arthroplasty		
Sample Size	40 participants/ 20 per group		
Planned Study Period	12 months total length/ individual participant involvement 3 months		
Planned Recruitment period	01/03/2020 to 01/09/2020		
	Objectives	Outcome Measures	Time point(s)
Primary	To test the procedures and processes of the trial and to estimate parameters for the main trial sample size calculation	
 • Berg Balance Scale • Participant recruitment figures • Participant retention figures • Number of protocol violations • BW programme diary • Qualitative interviews 	Baseline and 3 months
Secondary	To examine the consistency of the effects of the backwards walking programme on falls risk, balance, strength and gait speed following hip and knee joint arthroplasty	
 • Four Square Step Test • 2 minute walk test • 30 second stand test • Activities-specific Balance confidence scale • Falls diary 	Baseline and 3 months
Intervention(s)	A 12 week backward walking programme alongside a standard course of physiotherapy		
Comparator	Standard course of physiotherapy		

4. ABBREVIATIONS

CI	Chief Investigator
CRF	Case Report Form
CTRG	Clinical Trials & Research Governance, University of Oxford
GCP	Good Clinical Practice
GP	General Practitioner
HRA	Health Research Authority
ICF	Informed Consent Form
NHS	National Health Service
RES	Research Ethics Service
OXTREC	Oxford Tropical Research Ethics Committee
PI	Principal Investigator
PIL	Participant/ Patient Information Leaflet
R&D	NHS Trust R&D Department
REC	Research Ethics Committee
SOP	Standard Operating Procedure

5. BACKGROUND AND RATIONALE

In recent years the number of elective hip and knee joint arthroplasties has been steadily increasing with the National Joint Registry reporting 97,792 primary hip replacements and 102,944 primary knee replacements were carried out in the year 2018 alone¹. Older patients who have undergone a Total Hip Arthroplasty (THA) or Total Knee Arthroplasty (TKA) or Uni-compartmental Knee Arthroplasty (UKA) are known to be at an increased risk of falls. Studies have reported an incidence rate of falls of up to 40%² following TKA and 36% post THA³ whereas the prevalence of falls for community dwelling older adults is 28%⁴. This increase in risk of falls for patients following joint arthroplasty is thought to be present due to the reduction in joint proprioception and a short term increase in pain alongside a reduction in muscle strength^{2,5}. These factors in combination with hospital admission itself predispose those older adults who are likely to have less physical reserves than their younger counterparts to falls⁶.

Falls have a multifactorial aetiology and there are several physiotherapy interventions developed to help target these contributing factors including gait re-education and strength and balance training⁷. However, the majority of conventional physiotherapy programmes currently fail to include a backwards

walking (BW) element to improve balance and decrease the risk of falls. The ability to take multi directional protective steps when exposed to forward, backward and lateral perturbations can decrease your risk of falls. However to effectively sustain balance, steps must be appropriately directed, timed, and executed to arrest the motion of the body's centre of mass by altering the base of support⁸. Without practice of BW patients following joint arthroplasty with their known reduction in strength and proprioception are less likely to be able to take a protective backwards step to prevent falls.

BW is a form of closed kinetic chain exercise which is known to be more functional, safe and effective than open kinetic chain exercises due to the reduced compressive forces at the patellofemoral joint⁹. Compared to forward walking, lower limb muscle activity during backward walking is greater due to the higher recruitment of motor units¹⁰. In addition, BW has been seen to increase cardio-pulmonary demand¹¹ helping to improve the cardiovascular fitness of patients. The absence of visual cues also increases the spatial and temporal gait parameters¹². BW does not require any specific equipment thus is a cost effective and easy mode of rehabilitation. Additionally once it has been completed under supervision a BW programme can be continued as part of a home exercise programme. Taking into consideration all of these factors BW could form an important functional and strengthening role in the rehabilitation of patients post THA and TKA/UKA.

There have been a number of studies looking at BW for different musculoskeletal conditions. A recent literature review and meta-analysis concluded that although there was sufficient evidence to recommend a BW programme as part of a rehabilitation programme for patients with knee osteoarthritis, other conditions still required further evidence¹³. Patients following hip and knee arthroplasty differ from the populations with knee OA as they have greater strength deficits¹⁴ and lower activity levels post operatively¹⁵ making them more at risk of falls. To date there are no randomised controlled trials (RCT) looking at a BW programme for this population. It is therefore pertinent that we look at the effectiveness of BW post hip and knee arthroplasty in reducing the risk of falls and improving balance and physical function in a RCT. This feasibility pilot will be the first step to delivering the RCT and will test the procedures and acceptability of a BW programme for patients following THR/TKA/UKA.

6. OBJECTIVES AND OUTCOME MEASURES

Objectives	Outcome Measures	Timepoint(s) of evaluation of this outcome measure (if applicable)

Primary Objective To test the procedures and processes of the trial and to estimate parameters for the main trial sample size calculation
	
 • Berg Balance Scale (BBS) (to calculate sample size) – Static and dynamic balance activities of varying difficulty are performed to provide a measure of falls risk and balance • Participant recruitment figures • Participant retention figures • Randomisation acceptability • Number of protocol violations from fidelity checks • BW programme diary to provide a measure of adherence • Participant safety through recording any falls and injuries whilst completing the BW programme • Qualitative interviews to determine acceptability of intervention and delivery with participants and physiotherapists 	Baseline and 3 months

Secondary Objectives To examine the consistency of the effects of the backwards walking programme on falls risk, balance, strength and gait speed following hip and knee joint arthroplasty
	
 • Four Square Step Test (FSST)- a test of dynamic balance that clinically assesses a person's ability to step over objects forward, sideways, and backwards • 2 minute walk test (2MWT)- assesses walking distance • 30 second chair rise test - assesses sit to stand ability and provides a measure of lower limb strength and dynamic balance. • Activities-specific Balance confidence scale (ABC) - self-reported measure of confidence in performing various ambulatory activities without falling • Falls diary - records the frequency of falls 	Baseline and 3 months

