9.6.2. Description of comparator(s)

This group will undertake a routine course of one to one out-patient physiotherapy over 12 weeks. To allow comparison between the two groups the control group will also have up to four review appointments where their home exercise programme can be progressed or regressed. The physiotherapy treatments will not be restricted (apart from no BW programme) to allow for a pragmatic approach based on the treating clinician's clinical judgement, however their content will be recorded on treatment logs.

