9.8. Subsequent Visits

As this is a feasibility pilot study the main aims are not to assess the effectiveness of the intervention but to trial the acceptability and feasibility of the study protocol and pilot its delivery at the Nuffield Orthopaedic Centre in Oxford. For this reason the main assessments for the study relate to recruitment, retention and acceptability. The research clinician will therefore collect data throughout the trial on the number of patients screened, the number that consented, the reason for not consenting, the number of drop outs, the availability of the outcome measure data and the standard deviation of the BBS in order to estimate the sample size. The acceptability of the intervention will be measured through collection of the BW programme diary which will provide a measure of adherence. Participants will also be invited to take part in an interview to determine the study acceptability.

Fidelity checks

Fidelity checks will be made by a member of the study team who is not blinded to treatment allocation to ensure adherence to the study protocol from the recruiting and treating clinicians. These will take place mid-way through study recruitment once approximately 20 participants have been randomised.

12 week follow up

Participants will be followed up at 12 weeks for the final assessment. Participants will be asked to return to the physiotherapy clinic or where possible this appointment will tie in with their final physiotherapy appointment at 12 weeks. The outcome measure assessments will be the same as at baseline and the research clinician will ensure they collect in the falls diary and if applicable BW programme diary.

Qualitative interviews

Patients taking part in the study, and treating clinicians, will be invited to take part at the in a semi-structured interview to determine if the study procedures and trial design were acceptable to participants. This will take place after the participants have completed their 12 week follow up and physiotherapists have completed the intervention delivery.

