11.2. Description of the Statistical Methods

This is a feasibility pilot RCT, therefore the aim of this study is not to provide a measure of efficacy but to determine whether it is possible to run a large scale RCT. Participant demographics will be summarised using standard descriptive statistics. The following components will also be analysed:

- The mean and SD of the primary outcome measure the BBS will be analysed to provide a sample size calculation for a larger RCT
- Recruitment – The number of recruited participants in the recruitment window, the number of participants screened to allow for the recruitment target to be met and the reason for non-entry into the trial which will provide realistic expectations of recruitment for a future larger scale RCT.
- Randomisation – Is randomisation acceptable to participants in this study? Does randomisation create comparable groups?
- Intervention acceptability – Is the intervention acceptable to participants? Do any participants fail to complete the intervention? Adherence to the prescribed BW programme will be measured through a collection of a diary. These issues will also be explored in more depth as part of the qualitative study.
- Retention of participants – Drop outs and wherever possible the reason for drop out will be recorded.
- Fidelity - Fidelity checks will be conducted, this will involve observing treatment sessions to check adherence to the protocol.

Qualitative interviews:

The data from the interviews will be analysed using thematic analysis, using six steps proposed by Braun and Clarke transcribing the data, generating initial codes, searching for themes, reviewing themes, defining and naming themes and producing the report. Data will be transcribed from the audio recordings, whilst initial ideas are recorded. Then data will then be coded, before codes are grouped into themes. To aid the process of data analysis NVIVO 10 (or later version) software will be used, this computer programme is designed for the analysis of qualitative data. It allows the collection, sorting and analysing of data from qualitative methods such as interviews.

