14. PROTOCOL DEVIATIONS

A study related deviation is a departure from the ethically approved study protocol or other study document or process (e.g. consent process or administration of study intervention) or from Good Clinical Practice (GCP) or any applicable regulatory requirements. Any deviations from the protocol will be documented in a protocol deviation form and filed in the study master file.

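### The protocol-violation outcome is a partial count with no denominator, drawn from one mid-recruitment window, and it leaves out the whole-trial deviation forms and control-arm logs the study already keeps

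*Combined protocol and SAP*

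**What the plan says.** The synopsis (section 3) lists "Number of protocol violations" as a primary outcome and does not restrict its source. Section 6 does restrict it: "Number of protocol violations from fidelity checks". The timepoint beside the primary outcomes in section 6 is "Baseline and 3 months".

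Section 9.8 says of the fidelity checks: "These will take place mid-way through study recruitment once approximately 20 participants have been randomised". Their stated purpose there is "to ensure adherence to the study protocol from the recruiting and treating clinicians". Section 11.2, which serves as the analysis plan because section 11.1 says there is no separate one, describes them in one line: "this will involve observing treatment sessions to check adherence to the protocol".

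Two other records bear on the same question. Section 14 says: "Any deviations from the protocol will be documented in a protocol deviation form and filed in the study master file". For control sessions, section 9.6.2 says "their content will be recorded on treatment logs". Section 11.2 uses neither record.

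**The concern.** The pilot exists to tell a main trial whether its procedures work, and this outcome is the one that counts failures of procedure. As defined, it counts only what an observer sees in an unspecified set of sessions during one window. A low figure could mean good fidelity or little observation. The figure could be zero while deviation forms sit in the master file.

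The planned difference between the arms is the BW programme: controls may receive any physiotherapy except that. How often controls are given BW anyway, and how often intervention participants are never prescribed it, is what a main trial would most want to know. A count without a denominator cannot say.

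**Working it through.** **1. The sources side by side**

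| Item | Section 3 | Section 6 | Section 9.8 | Section 11.2 | Section 14 |
|---|---|---|---|---|---|
| Source of count | not limited | fidelity checks only | – | – | separate forms, not linked |
| Timing | baseline and 3 months | baseline and 3 months | about 20 randomised | – | any time |
| Whose conduct | – | – | recruiters and therapists | treatment sessions only | anyone |
| Denominator or number observed | none | none | none | none | none |

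Three mismatches follow. The synopsis and section 6 give different scopes. Section 9.8 includes recruiting clinicians, but section 11.2 gives no method that could show a screening, consent or allocation error. The timepoint does not fit a mid-recruitment check (the column heading in section 6 does say where applicable).

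**2. The plan's own figure**

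Mid-way through recruitment of 40 is 40 / 2 = 20, which agrees with section 9.8. About 40 − 20 = 20 participants are therefore randomised after the window opens, and no later check is described.

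**3. How many sessions there could be**

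Inputs: 40 participants (section 11.3) and a maximum of four reviews in each arm (sections 9.6.1 and 9.6.2). One initial session per participant is named for the intervention arm and assumed for controls.

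- Maximum with the initial session: 40 × (1 + 4) = 200.
- Reviews only: 40 × 4 = 160.

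The number to be observed, m, is not given, so the coverage m / 200 cannot be computed from the documents. The values of m below are assumptions.

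**4. What a given count would mean**

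Sessions are treated as independent. If no violation is seen in m sessions, the one-sided 95% upper limit on the per-session rate is 1 − 0.05^(1/m). If the true rate is an assumed 10%, the chance of seeing at least one violation is 1 − 0.9^m.

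| m (assumed) | m / 200 | Upper limit if 0 seen | Chance of seeing ≥ 1 at a 10% rate |
|---|---|---|---|
| 5 | 2.5% | 45% | 41% |
| 10 | 5% | 26% | 65% |
| 20 | 10% | 14% | 88% |
| 40 | 20% | 7% | 98% |

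Likewise, three sessions with a violation could be 3/5 = 60% (exact 95% CI 15% to 95%) or 3/40 = 7.5% (1.6% to 20%). Sessions cluster within participants and therapists, so the real uncertainty is likely to be wider.

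**The case against.** The strongest reply is that this is one of eight descriptive measures under the primary objective, with no test or progression rule resting on it. A mid-way check can also be partly corrective, which makes its timing reasonable. Section 6 labels its source openly, and nothing says the number of sessions observed will be withheld. The figures above rest on assumed numbers and show only that small samples are imprecise. All of that is fair, and it limits the weight of the point. It does not remove it: the plan names a source for the outcome, and that source leaves out whole-trial records already being kept.

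Several stronger readings are tempting but not supported:

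- **A single observation that misses most sessions.** Section 9.8 speaks of checks in the plural, within one window. Their number is unstated, so low coverage is an inference.
- **Recruitment is not checked at all.** Section 9.8 includes recruiting clinicians, and section 11.2 does not say that observation is the only component. What is missing is a stated method.
- **Observation would miss BW in a control session.** Watching a session is a direct way to see it. The limit is how many sessions are watched.
- **Missed assessments enter no outcome.** Section 9.8 collects the completeness of outcome data along with screening, consent and drop-out numbers. Section 9.4 also keeps a log of every allocation.
- **The safety halt prevents the check.** A halt after the tenth intervention participant would fall near 20 randomised, but it pauses recruitment. Nothing in section 7 says that treatment of those already enrolled stops, so sessions could still be observed.
- **The trial cannot show whether its protocol was followed.** The deviation forms, treatment logs and BW diary all bear on this. The limitation belongs to this count alone.

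**Conclusion.** The point holds for the outcome as defined. It is a partial sample from one window, without a denominator, and it excludes the section 14 forms and the control-arm treatment logs. It cannot give a trial-wide violation figure and may look falsely favourable. The gap lies in the definition and reporting of the outcome; the deviations themselves are recorded.

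The size cannot be fixed from the documents because the number of sessions observed is not stated. Across an assumed 5 to 40 sessions, a count of zero leaves per-session rates of up to 45% down to 7% open, on the independence assumption. This illustrates the difficulty and does not predict the result. The change should be made, but no efficacy conclusion depends on it.

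**What to change.** Amend sections 6 and 11.2, and bring sections 3 and 9.8 into line.

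1. Make the outcome all deviations on section 14 forms over the whole trial, reported per randomised participant, by arm and by stage (screening, consent, allocation, treatment, assessment). Deviations before randomisation have no arm and should be shown by stage only.
2. Report fidelity-check violations separately, always with the number of sessions observed, by arm. State how recruiting clinicians are checked.
3. From the control-arm treatment logs, report the number and proportion of control participants with any BW programme recorded. For the intervention arm, report the proportion with no BW programme prescribed, where the records show it. The wording of section 9.6.1 leaves unclear whether intervention logs record BW itself, so this should be confirmed.
4. Give one scope and one timepoint for the outcome throughout.

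Item 3 is a participant-level summary. Absence of BW from an individual intervention session should not be counted as a violation: section 9.6.1 has the programme prescribed by the physiotherapist and done at home, and does not require it in every session. The logs are presumably completed by the treating therapists, so the observed sessions in item 2 remain useful as a more independent check.

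The cost is revised wording, some tabulation of existing records and a violation figure that is likely to be higher. No visits are added.

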7. STUDY DESIGN

This study is a mixed methods design. The quantitative study will be a randomised single blinded design. Up to 40 participants will be recruited from a single site at the Nuffield Orthopaedic Centre in Oxford. After recruitment baseline outcome measures will be taken. Block randomisation will then be used to balance stratification factors (hip or knee arthroplasty) into either the intervention or control group. The participant will receive their physiotherapy intervention or control at the Nuffield Orthopaedic Centre which will last up to 12 weeks. Once the first 5 participants randomised into the intervention arm have been recruited the study will be halted whilst all adverse event data is collected to ensure participants have not fallen when completing the intervention. If the study team is happy the intervention is not causing any adverse events, then the next five participants will be recruited and again the study will halt whilst their adverse event data is collected. This will continue until all 20 participants for the intervention group are recruited. Outcome measures will be repeated at 12 weeks once the treatment has ceased. This will be the final data collection point for the study.

The qualitative element of the study will involve semi structured interviews. This will take place after the participants have completed their 12 week follow up and physiotherapists have completed the intervention delivery. We will interview to a point of theoretical saturation¹⁶, and anticipate that up to 10 participants and 5 physiotherapists will allow us to develop useful themes.

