9. PROTOCOL PROCEDURES

9.1. Recruitment

Patients who have had a hip or knee replacement at the Nuffield Orthopaedic Centre in Oxford attend a 6 week post discharge clinic appointment. These patients will be screened for eligibility by their direct care team (Nuffield Orthopaedic Centre Physiotherapists). They will be introduced to the study by either a letter in the post from their direct care team (which will be sent alongside their clinic appointment letter) with information about the study and invitation letter and reply slip, or they will be introduced to the study and given the study information by their direct care team during their routine clinical appointment. Patients will be given ample time to consider taking part in the study. If they express an interest in the study the investigator will review the study details and answer any questions they may have. They will then be screened for eligibility and those who meet the criteria will take part in the study. If they agree to take part an appointment will be made to obtain consent and record baseline data and outcome measures with a trial research clinician at the Nuffield Orthopaedic Centre. Once patients have completed their baseline assessment they will be randomised according to the procedure set out below. Those who do not wish to take part will be asked if they can provide a reason for declining so that recruitment onto the trial can be analysed. The trial research clinician will also record the number of responders to the study information. As detailed in the study design section after the first 5 participants have been recruited to the intervention arm the study will stop whilst adverse event data is collected to ensure participants are not falling during the intervention. Providing this is not the case the study will resume and continue to stop and evaluate adverse event data for every 5 participants in the intervention arm.

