30s Chair rise test – This is a validated clinical measure of lower body strength and dynamic balance which is recommended as one of the best physical performance tests following joint arthroplasty by OARSI²². The participant is asked to sit in a straight back chair of 17" seat height without arms. From the sitting position, the participant stands up completely up so hips and knees are fully extended, then completely back down, so that the bottom fully touches the seat. This is repeated for 30 seconds and the participant should not use their hands to get up. If the participant is unable to do this they are allowed to place their hands on their knees or use their regular mobility aid to rise from the chair and this is recorded as an adapted score.

Following the collection of the physical outcome measures the participants will be asked to complete the ABC questionnaire. This provides a measure of balance confidence whilst performing certain tasks and is a 16 item self-report measure. Each question is scored out of 100 with 0 representing no confidence and 100 representing total confidence. The average of all scores is used to provide a final score and normative data is available for older adults²³.

At the end of the assessment the participant will be issued with a falls diary to complete for the 3 months whilst they are taking part in the study. For those randomised to the intervention arm a diary of adherence to the BW programme will also be issued at the initial physiotherapy appointment.

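### The listed safety outcome and the staged safety reviews cover the intervention arm only, and falls data collected in both arms are linked to neither

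*Combined protocol and SAP*

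**What the plan says.** The section 6 table places one safety item under the primary objective: "Participant safety through recording any falls and injuries whilst completing the BW programme". The synopsis list of primary outcomes omits it. Under the secondary objective, which concerns the programme's effects on falls risk and related measures, the same table has "Falls diary - records the frequency of falls".

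Section 7 pauses the study after each five intervention participants while "all adverse event data is collected to ensure participants have not fallen when completing the intervention". It resumes if the study team is satisfied that the intervention is not the cause of adverse events. Section 9.1 repeats the arrangement: recruitment will "continue to stop and evaluate adverse event data for every 5 participants in the intervention arm". Neither section mentions control participants.

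Section 9.6.2 excludes a BW programme from the comparator. Section 9.7 gives every participant the falls diary at baseline: "the participant will be issued with a falls diary to complete for the 3 months whilst they are taking part in the study". The BW diary is separate: "For those randomised to the intervention arm a diary of adherence to the BW programme will also be issued at the initial physiotherapy appointment". At 12 weeks, under section 9.8, "the research clinician will ensure they collect in the falls diary and if applicable BW programme diary".

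Section 10 sets a safety window from consent to completion for all participants, but defines and reports only serious events. Section 11.1 says there is no separate SAP, and section 11.2 has no line for falls, injuries or adverse events.

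**The concern.** The pilot tests a home programme in patients whom section 5 describes as at raised risk of falling. The studies behind it, according to section 9.6.1, were all supervised. Whether falls and injuries look acceptable is therefore one of the main things a larger trial will need to know.

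The safety item cannot be contrasted between arms, because controls cannot have the event. The reviews nevertheless call for a causal judgement. Two opposite errors follow. If only falls during BW sessions count, falls between sessions are missed, including any that the programme contributes to. If all falls in the intervention arm count, ordinary background falls may be taken for harm because nothing stands beside them. The control-arm diary could guard against both errors, but the plan connects it neither to the safety item nor to the reviews, and specifies no by-arm summary.

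**Working it through.** **1. Which arm each element covers**

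| Element | Section | Arms | Tied to BW? | Analysis planned in 11.2? |
|---|---|---|---|---|
| Safety item (primary objective) | 6 | Intervention only | Yes | No |
| Staged reviews | 7, 9.1 | Intervention only | Yes | No |
| Falls diary (secondary objective) | 6, 9.7, 9.8 | Both | No | No |
| Serious adverse events | 10 | Both | No | No |

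The wording of the safety item is ambiguous. The synopsis and section 9.6.1 use the programme to mean the 12-week course, while section 9.6.1 also uses it for a single daily session. The section 7 phrase about having fallen when completing the intervention favours the session reading. The arm coverage is the same either way.

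**2. Background falls among 5 participants**

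Inputs: p = 0.28 (community-dwelling older adults), 0.36 (after hip replacement) and 0.40 (upper figure after knee replacement), all from section 5, with no time window given. Five participants per review stage come from sections 7 and 9.1.

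Assumptions: the window T is 52 or 26 weeks, the hazard is constant, the programme has no effect, and all five are observed for a full 12 weeks.

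- 12-week risk: r = 1 − (1 − p)^(12/T)
- Chance of at least one faller among 5: 1 − (1 − r)^5
- Expected fallers among 20: 20r

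| T | p | r | At least one of 5 | Expected among 20 |
|---|---|---|---|---|
| 52 weeks | 0.28 | 0.073 | 32% | 1.5 |
| 52 weeks | 0.36 | 0.098 | 40% | 2.0 |
| 52 weeks | 0.40 | 0.111 | 45% | 2.2 |
| 26 weeks | 0.28 | 0.141 | 53% | 2.8 |
| 26 weeks | 0.36 | 0.186 | 64% | 3.7 |
| 26 weeks | 0.40 | 0.210 | 69% | 4.2 |

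Worked line: 1 − 0.72^(12/52) = 0.073, and 1 − 0.927^5 = 0.32.

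If the cited figures were already 3-month risks, the chance among 5 would be 81% (1 − 0.72^5) to 92% (1 − 0.60^5). A review held before 12 weeks have passed would see fewer events.

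**3. What a by-arm comparison could show**

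Section 11.3 gives 20 per group, and 2 × 20 = 40 agrees with the stated total. The approximate 95% half-width for a difference in the proportion who fall is 1.96 × √(2r(1 − r)/20).

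- r = 0.073: 16 percentage points
- r = 0.210: 25 percentage points
- r = 0.40 (3-month reading): 30 percentage points

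Taking the cited figures as 3-month risks, power to detect a doubling (two-sided 5%, normal approximation) is 43% to 75%. Taking them as 12-month risks, with a quarter of a year at risk (7.9% to 12.0%), it is 12% to 16%. Fisher's exact test gives 31% to 65% and 5% to 9%. The comparison is descriptive under every reading.

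**The case against.** The strongest reply is that the trial already collects what is needed. Every participant keeps a falls diary for the whole period, it sits under an objective that names falls risk, section 7 collects all adverse event data, and the section 10 window is not restricted by arm. This stands against several stronger readings that a reader might infer:

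- *The trial cannot compare falls between arms.* It can. Silence in section 11.2 is not a decision to omit the comparison. The gap is that none is specified.
- *Safety is watched for only about 1% of the day.* Ten minutes in an assumed 16-hour waking day is 10/960 = 1.0%. That needs the session-only reading, which the wording does not settle, and share of time is not share of risk.
- *A fall later the same day is not a safety event.* The course reading, and the collection of all adverse event data, could both include it.
- *The diary does not record injury or circumstances.* The form is not in the documents, and one line about frequency does not show what it leaves out.

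It is also fair that the probabilities above concern all-cause falls, whereas the reviews are worded around falls during the intervention. They show why one-arm all-cause data would be hard to read. They do not estimate how often the reviews as worded would raise a concern. Finally, this is a feasibility study that disclaims efficacy, so low power is no fault in itself.

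What survives is that the safety item is one-armed on either reading, the reviews ask a causal question without a comparator, and no safety or falls summary is planned.

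**Conclusion.** The point holds as a gap in definition and reporting that is cheap to close. It is not a lack of control-arm falls data. The safety outcome and the reviews should draw on the diary that both arms already keep.

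The size is indicative only. With 12- or 6-month windows, constant hazard and a full 12 weeks of observation, one or more background fallers among 5 participants has a chance of about 32% to 69%, with 1.5 to 4.2 expected among the 20 intervention participants. The lower end of each range uses a community figure and the upper end an after-knee-replacement figure, so the range spans different populations. That the safety item covers one arm only depends on none of these assumptions.

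**What to change.** - **Section 6:** define safety as all falls and all injuries in both arms, from consent to the end of follow-up, with events during BW sessions reported as a subset. This also removes the ambiguity in the wording.
- **Falls diary:** if it does not already do so, have it record injury (yes/no) and the activity at the time, in the same form for both arms. The detail must be enough to identify BW, for example a free-text activity field or a clarifying question when a fall is reported. A choice between home exercise and other would not do, because intervention participants also do other prescribed exercises at home.
- **Sections 7 and 9.1:** at each staged review, show the falls and adverse events known so far for control participants beside the intervention data, with person-weeks per arm.
- **Section 11.2:** add a descriptive by-arm summary of participants who fell, number of falls and injurious falls, with person-time and exact intervals.

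The cost is wording in four sections, a slightly longer diary, and possibly some interim collection of control falls, since diaries are otherwise returned at 12 weeks. No extra participants are needed. The comparison will be imprecise and should be described that way. No stopping rule is proposed.
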